# keep/discard original items and nvalid vars
if (keep == FALSE) {
  data <- data %>% select(-all_of(items), -starts_with('nvalid.'))
} else {
  data <- data
}
# Rounding
if (is.numeric(digits) == TRUE) {
  data <- data %>% mutate_at(vars(starts_with('score')), list(~ round(., digits)))
} else {
  data <- data
}
}
data
}

```

## 6.7 Code for determining the FCQ-T-r score

The score is introduced in Meule et al. (2014) and the cut-off in Meule (2018).

```

scoring_fcqtr <- function(data, items = 1:15, keep = TRUE,
                          nvalid = list(
                            sum = 12
                          ),
                          digits = NULL) {

  if (min(data[, items], na.rm = T) < 1) {
    stop("Minimum possible value for BISBAS items is 1")
  } else if (max(data[, items], na.rm = T) > 6) {
    stop("Maximum possible value for BISBAS items is 6")
  }
  # check for number of specified items
  if (length(items) != 15) {
    stop("Number of items must be 15!")
  }
  items.sum <- items[1:15]
  data <- data %>%
  mutate(
    nvalid.fcqtr.sum = rowSums(!is.na(select(., all_of(items.sum)))),
    score.fcqtr.sum = 15*rowMeans(select(., all_of(items.sum)), na.rm = TRUE),
    score.fcqtr.sum = ifelse(nvalid.fcqtr.sum >= nvalid[['sum']], score.fcqtr.sum, NA),
    cutoff.fcqtr.sum = case_when(
      score.fcqtr.sum <50 ~ "no food addiction",
      score.fcqtr.sum >=50 ~ "food addiction"
    ),
    cutoff.fcqtr.sum = factor(cutoff.fcqtr.sum, levels=c("no food addiction", "food
addiction"))
  )
  # keep/discard original items and nvalid vars
  if (keep == FALSE) {
    data <- data %>% select(-all_of(items), -starts_with('nvalid.'))
  }
}

```

```

} else {
  data <- data
}
# Rounding
if (is.numeric(digits) == TRUE) {
  data <- data %>% mutate_at(vars(starts_with('score')), list(~ round(., digits)))
} else {
  data <- data
}

data
}

```

## 6.8 Code for determining the PHQ-D score

The score is discussed in the following articles (Spitzer et al. 1999; Kroenke et al. 2010)

```

function (data, items = 1:9, keep = TRUE, nvalid = 7, digits = NULL)
{
  library(dplyr, warn.conflicts = FALSE)
  if (min(data[, items], na.rm = T) < 0) {
    stop("Minimum possible value for PHQ-9 items is 0")
  }
  else if (max(data[, items], na.rm = T) > 3) {
    stop("Maximum possible value for PHQ-9 items is 3")
  }
  if (length(items) != 9) {
    stop("Number of items must be 9!")
  }
  items <- items
  data <- data %>%
    mutate(nvalid.phq9 = rowSums(!is.na(select(., items))),
           mean.temp = rowSums(select(., items), na.rm = TRUE)/nvalid.phq9) %>%
    mutate_at(vars(!!!items), list(~ifelse(is.na(.), mean.temp, .))) %>%
    mutate(score.temp = rowSums(select(., items), na.rm = TRUE),
           score.phq9 = ifelse(nvalid.phq9 >= nvalid,
                                score.temp, NA), cutoff.phq9 = case_when(score.phq9 >= 20 ~ "Severe",
                                score.phq9 >= 15 ~ "Moderately Severe", score.phq9 >= 10 ~ "Moderate",
                                score.phq9 >= 5 ~ "Mild", score.phq9 < 5 ~ "Minimal"),
           cutoff.phq9 = factor(cutoff.phq9, levels = c("Minimal", "Mild", "Moderate",
                                                       "Moderately Severe", "Severe")))%>%
    select(-mean.temp, -score.temp)
  if (keep == FALSE) {
    data <- data %>% select(-items, -nvalid.phq9)
  }
  else {
    data <- data
  }
  if (is.numeric(digits) == TRUE) {
    data <- data %>% mutate_at(vars(score.phq9), list(~round(.,
                                                         digits)))
  }
  else {
    data <- data
  }
  data
}

```

## 6.9 Code for determining the PHQ-A score

The PHQ-A (also referred to as GAD-7, general anxiety disorder) score is derived from the PHQ questionnaire and was introduced in Spitzer et al. (2006) and an algorithm for missing values can be found in Teymoori et al. (2020).

```

scoring_gad7 <- function(data, items = 1:7, keep = TRUE, nvalid = 6, digits = NULL) {
  if (min(data[, items], na.rm = T) < 0) {
    stop("Minimum possible value for PHQ-9 items is 0")
  } else if (max(data[, items], na.rm = T) > 3) {
    stop("Maximum possible value for PHQ-9 items is 3")
  }
}

```

```

# check for number of specified items
if (length(items) != 7) {
  stop("Number of items must be 7!")
}
items <- items
data <- data %>%
  mutate(
    nvalid.gad7 = rowSums(!is.na(select(., items))),
    score.gad7 = 7*rowMeans(select(., items), na.rm = TRUE),
    score.gad7 = ifelse(nvalid.gad7 >= nvalid, score.gad7, NA),
    cutoff.gad7 = case_when(
      score.gad7 >= 15 ~ "Severe",
      score.gad7 >= 10 ~ "Moderate",
      score.gad7 >= 5 ~ "Mild",
      score.gad7 < 5 ~ "Minimal"
    ),
    cutoff.gad7 = factor(cutoff.gad7, levels = c("Minimal", "Mild", "Moderate", "Severe"))
  )
# Keep single items and nvalid variables
if (keep == FALSE) {
  data <- data %>% select(-items, -nvalid.gad7)
} else {
  data <- data
}
# Rounding
if (is.numeric(digits) == TRUE) {
  data <- data %>% mutate_at(vars(score.gad7), list(~ round(., digits)))
} else {
  data <- data
}
data
}

```

## 6.10 Code for determining the SF-12 scores

The following code follows the standard described in (Stieglitz 1999).

```

scoring_sf12 <- function(data, items = 1:12, keep = TRUE, digits = NULL) {
  if (min(data[, items], na.rm = T) < 0) {
    stop("Minimum possible value for SF-12 items is 0")
  } else if (max(data[, items], na.rm = T) > 6) {
    stop("Maximum possible value for SF-12 items is 6")
  }
  # check for number of specified items
  if (length(items) != 12) {
    stop("Number of items must be 12!")
  }
  items.rev6 <- items[c(1,8)]
  items.rev7 <- items[c(9,10)]
  data <- data %>%
    mutate_at(vars(all_of(items.rev6)), list(~ 6 - .)) %>%
    mutate_at(vars(all_of(items.rev7)), list(~ 7 - .))
  physical <- 56.57706 +
    Recode(data[,items[1]], "1= -8.37399; 2= -5.56461; 3= -3.02396; 4= -1.31872; 5=0") +
    Recode(data[,items[2]], "1= -7.23216; 2= -3.45555; 3=0") +
    Recode(data[,items[3]], "1= -6.24397; 2= -2.73557; 3=0") +
    Recode(data[,items[4]], "1= -4.61617; 0=0") +
    Recode(data[,items[5]], "1= -5.51747; 0=0") +
    Recode(data[,items[6]], "1= 3.04365; 0=0") +
    Recode(data[,items[7]], "1= 2.32091; 0=0") +
    Recode(data[,items[8]], "1= -11.25544; 2= -8.38063; 3= -6.50522; 4= -3.80130; 5=0") +
    Recode(data[,items[9]], "1= 3.46638; 2= 2.90426; 3= 2.37241; 4= 1.36689; 5= 0.66514;
6=0") +
    Recode(data[,items[10]], "1= -2.44706; 2= -2.02168; 3= -1.61850; 4= -1.14387; 5= -0.42251;
6=0") +
    Recode(data[,items[11]], "1= 4.61446; 2= 3.41593; 3= 2.34247; 4= 1.28044; 5= 0.41188;
6=0") +
    Recode(data[,items[12]], "1= -0.33682; 2= -0.94342; 3= -0.18043; 4= 0.11038; 5=0")
  mental <- 60.75781 +
    Recode(data[,items[1]], "1= -1.71175; 2= -0.16891; 3= 0.03482; 4= -0.06064; 5=0") +
    Recode(data[,items[2]], "1= 3.93115; 2= 1.8684; 3=0") +

```

```
Recode(data[,items[3]], "1= 2.68282; 2= 1.43103; 3=0") +
Recode(data[,items[4]], "1= 1.44060; 0=0") +
Recode(data[,items[5]], "1= 1.66968; 0=0") +
Recode(data[,items[6]], "1= -6.82672; 0=0") +
Recode(data[,items[7]], "1= -5.69921; 0=0") +
Recode(data[,items[8]], "1= 1.48619; 2= 1.76691; 3= 1.49384; 4= 0.90384; 5=0") +
Recode(data[,items[9]], "1= -10.19085;2= -7.92717; 3= -6.31121; 4= -4.09842; 5= -1.94949;
6=0") +
Recode(data[,items[10]],"1= -6.02409; 2= -4.88962; 3= -3.29805; 4= -1.65178; 5= -0.92057;
6=0") +
Recode(data[,items[11]],"1= -16.15395;2=-10.77911; 3= -8.09914; 4= -4.59055; 5= -1.95934;
6=0") +
Recode(data[,items[12]],"1= -6.29724; 2= -8.26066; 3= -5.63286; 4= -3.13896; 5=0")
# Keep single items
if (keep == FALSE) {
  data <- data %>% select(-items)
} else {
  data <- data
}
# Rounding
if (is.numeric(digits) == TRUE) {
  data$score.sf12.physical <- round(physical,digits)
  data$score.sf12.mental <- round(mental,digits)
} else {
  data$score.sf12.physical <- physical
  data$score.sf12.mental <- mental
}
data
}
```

## 6.11 CRED-nf checklist

1 Domain	Item #	Checklist item	Planned analysis reported in section
Pre-experiment			
	1a	Pre-register experimental protocol and planned analyses	AO
	1b	Justify sample size	SP
Control groups			
	2a	Employ control group(s) or control condition(s)	AO
	2b	When leveraging experimental designs where a double-blind is possible, use a double-blind	NA
	2c	Blind those who rate the outcomes, and when possible, the statisticians involved	SP
	2d	Examine to what extent participants and experimenters remain blinded	NA
	2e	In clinical efficacy studies, employ a standard-of-care intervention group as a benchmark for improvement	SP
Control measures			
	3a	Collect data on psychosocial factors	2.3.1., A
	3b	Report whether participants were provided with a strategy	AO
	3c	Report the strategies participants used	AO
	3d	Report methods used for online-data processing and artifact correction	6.11.3., A
	3e	Report condition and group effects for artifacts	6.11.2., A
Feedback specifications			
	4a	Report how the online-feature extraction was defined	6.11.1., A

	4b	Report and justify the reinforcement schedule	6.11.3., 6.12.1., A
	4c	Report the feedback modality and content	6.11.3., A
	4d	Collect and report all brain activity variable(s) and/or contrasts used for feedback, as displayed to experimental participants	4.3.2., 5.3.2., A
	4e	Report the hardware and software used	6.11.1., 6.11.3., 6.12.1., A
Outcome measures			
Brain	5a	Report neurofeedback regulation success based on the feedback signal	4.3.1., 4.4.1., A
	5b	Plot within-session and between-session regulation blocks of feedback variable(s), as well as pre-to-post resting baselines or contrasts	4.3.2., 4.4.2., A
	5c	Statistically compare the experimental condition/group to the control condition(s)/group(s) (not only each group to baseline measures)	4.3.2., 4.4.2., A
Behaviour	6a	Include measures of clinical or behavioural significance, defined a priori, and describe whether they were reached	4.1., A
	6b	Run correlational analyses between regulation success and behavioural outcomes	4.3.3., 4.4.3., A
Data storage			
	7a	Upload all materials, analysis scripts, code, and raw data used for analyses, as well as final values, to an open access data repository, when feasible	NA

*Note.* Darker shaded boxes represent *Essential* checklist items; lightly shaded boxes represent *Encouraged* checklist items. Article only: the respective item will be covered in the article, but does not apply to the statistical analysis plan; A: article, AO: article only, NA: not applicable, SP: see study protocol.

## 6.11. fNIRS Data Preprocessing

### 6.11.1. Region of Interest Selection

Prior to the first NF session, participants underwent a Go/NoGo and a passive viewing task that served as a functional localizer to delineate individual brain regions implicated in cognitive control.

A general linear model (GLM) with the standard hemodynamic response function and two regressors corresponding to the Go/NoGo and NoGo Passive viewing condition, respectively, was applied. The resulting  $t$ -values of beta weights for the difference between conditions (Go/NoGo – NoGoPassive Viewing) were used to determine the primary location for the fNIRS NF process: the two adjacent channels that showed the highest  $t$ -values in the same direction with the same sign were selected.

### 6.11.2. Offline Analysis of fNIRS data ([name])

Offline analyses of fNIRS data were calculated with MATLAB R2020a using the Brain AnalyzIR Toolbox (Santosa et al. 2018); see Item 4e of the CRED-nf checklist). The following parts of the default pipeline were used:

#### Transformations

Individual differences in head circumference have been shown to have a negligible effect on how the probe is positioned over the cortical region of interest for each participant and will therefore not be considered (Okamoto et al. 2004). The baseline of raw data was trimmed to 30s before and after each NF trial. Data were converted to changes in optical density values over time using the toolbox's *OpticalDensity* function. The function used in the toolbox is given by  $\Delta OD(t) = -\log(I(t)/I_0)$  where  $I(t)$  is the intensity of the signal recorded and  $I_0$  is the mean reference signal intensity at baseline. The optical density values were converted to concentration changes using the modified Beer-Lambert law (via the toolbox's function *BeerLambertLaw*) under consideration of an age-dependent differential path length factor that is validated for frontotemporal regions (Scholkmann & Wolf 2013) and a partial path length factor. The age that is used for the calculation of this age-dependent differential path length factor was derived from the age at the first NF session.

#### First Level Analysis

A GLM was calculated for each channel, each half (first/second half of NF), each condition (feedback/transfer/mirror) and each session of each participant, modelling event-related concentration changes with a canonical hemodynamic response via the toolbox's function *GLM* (leaving the type at the default option AR-IRLS). The general linear equation was solved with an iteratively auto-regressive whitened, weighted least-squares method (AR-IRLS) (Barker et al. 2013). This model applies an  $n^{\text{th}}$ -order AR filter derived via an Akaike model-order selection to whiten both sides of the GLM expression. All source-detector pairs within a file are solved concurrently yielding a full covariance model of the noise. The AR-IRLS method accounts for the expected presence of serially correlated errors (i.e., extracerebral components) in the optical signals due to cardiac pulsation and respiration and has been shown to have a good control of type-I error (Huppert 2016). It is not recommended to filter data if using the AR-IRLS GLM algorithm (Huppert 2016). To ensure data quality, all data were visually inspected before and after applying the AR-IRLS method.

#### Outlier Removal

The toolbox offers the opportunity to automatically remove participants based on the leverage of the data in the *nirs.modules.RemoveOutlierSubjects*.

### 6.11.3. Online Analysis of fNIRS Data and Visual Feedback Signal

Turbo-Satori (TSI) 1.0.0. (BrainInnovation B.V., Maastricht, the Netherlands; Lührs & Goebel 2017; Item 4e) was used for real-time preprocessing. NIRStar 15.2. was connected to the NIRScout system via a universal serial bus cable and to TSI via a TCP/IP Ethernet connection.

The default settings of TSI were implemented as following: A GLM with ordinary least squares was fitted to the data. Raw wavelength data were detrended with a second-order moving average low-pass filter (cut-off 0.4Hz) to remove high-frequency noise (Item 3d of the CRED-nf checklist). These raw wavelength data were online converted to values of oxygenated and deoxygenated haemoglobin based on the modified Beer-Lambert law. In line with previous fNIRS NF studies, the feedback was based on the oxygenated haemoglobin signals. The NF signal was computed from the signal of the selected target channels by subtracting the baseline, which was set to the initial 20s of the experiment, from the currently scaled oxygenated haemoglobin value (Item 4a of the CRED-nf checklist).

### **Visual Feedback Signal**

The online feedback was visually displayed on the screen as an individually appetitive food picture via a python built-in function. The size of the picture visualized the neural activity level in the chosen region of interest channels continuously (Item 4b and Item 4c of the CRED-nf checklist). Precisely, the oxygenated hemoglobin value for the region of interest (i.e., the average of the two channels that were selected as region of interest) for a given time point was compared to the oxygenated hemoglobin value for the region of interest at the preceding time point. The goal in the NF task was to increase the oxygenated hemoglobin value. Thus, if the oxygenated hemoglobin value exceeded the previous value, the picture size was reduced by the constant factor 0.01, if the oxygenated hemoglobin value was less than the previous value, the picture size was increased by the constant factor 0.01. Each new picture (of a total of  $n = 12$  pictures) started with a picture size value of 1. The maximum picture size was defined by 1, the minimum picture size by 0.1. For these values, the picture size remained constant if participants decreased (for the maximum picture size) or increased (for the minimum picture size) their oxygenated hemoglobin value further. Nevertheless, these trials still count as success trials.

In the transfer condition, participants did not get real-time feedback. Instead, they were displayed the picture size they had reached by the final 2s of the experiment.

As outcome variable for the feedback condition, the minimum picture size, the mean picture size, and the percentage of successful trials were derived. For the transfer condition, the picture size displayed to the participants was derived as outcome variable.

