#### 4.3.1 Regulation success based on the feedback signal (CRED-nf 5a)

A graphical depiction for summary statistics of the raw data for each session in the regulation condition will be provided for the following variables

- percentage success defined to be the number of sample points with online oxygenated haemoglobin values were smaller than the predecessor divided by the total number of sampling points (roughly  $10^5$ ). This is a surrogate for the proportion of time for which the patient experienced “success” though a maximum/minimum picture size could not be exceeded and each step was so small that it could not be perceived.
- minimum picture size (12 per patient) as one measure of success for the feedback
- mean picture size (12 per patient) as a second measure of success for the feedback

Transfer condition

- a graphical representation as with the regulation condition will be provided

Note that after session 6, the selection of pictures was changed to avoid habituation effects.

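### SAP 6.11.3, read literally, scores falls in oxygenated haemoglobin at the maximum picture size as success, while SAP 4.3.1 defines percentage success in the opposite direction

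*SAP*

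**What the plan says.** SAP 6.11.3, under Visual Feedback Signal, states the direction of the task: "The goal in the NF task was to increase the oxygenated hemoglobin value". The picture follows that goal. It shrinks on a rise ("if the oxygenated hemoglobin value exceeded the previous value, the picture size was reduced by the constant factor 0.01") and grows on a fall ("if the oxygenated hemoglobin value was less than the previous value, the picture size was increased by the constant factor 0.01"). The limits are given as "The maximum picture size was defined by 1, the minimum picture size by 0.1", and each new picture "started with a picture size value of 1", which is the maximum.

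For the limits, the section says that the size "remained constant if participants decreased (for the maximum picture size) or increased (for the minimum picture size) their oxygenated hemoglobin value further". The next sentence is: "Nevertheless, these trials still count as success trials". The same section lists the percentage of successful trials as an outcome variable of the feedback condition, alongside minimum and mean picture size.

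SAP 4.3.1, which sets out the analysis, defines percentage success as the share of sampling points at which the online oxygenated haemoglobin value was below the value before it. It gives no scoring rule for the limits. It calls the measure a surrogate for the time during which the patient experienced success, with the reservation "though a maximum/minimum picture size could not be exceeded and each step was so small that it could not be perceived".

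**The concern.** The success sentence in 6.11.3 refers back to both limit cases. At the minimum size a further rise is a real success that the picture can no longer show. At the maximum size a further fall is a failure against the goal, yet it receives the same credit. Because each picture starts at the maximum, a patient who regulates poorly spends most of the time in the state that is scored wrongly.

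Section 4.3.1 does not resolve this. It counts falls, the opposite of the goal in 6.11.3, and it counts sampling points where 6.11.3 speaks of trials. A programmer working from the two sections could produce either of two different variables under one name, and neither would rise steadily with regulation.

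At stake is the per-session display of whether patients learned to regulate the signal, which the SAP offers as its answer to CRED-nf item 5a.

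**Working it through.** The documents state no value for this measure, so there is no figure of theirs to reproduce. The check works through the feedback rule itself.

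**Inputs from SAP 6.11.3:** start at size 1; maximum 1; minimum 0.1; step 0.01, read as addition or subtraction, so (1 − 0.1)/0.01 = 90 steps between the limits; a rise shrinks the picture and a fall enlarges it.

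**Assumptions:** each sampling point is a rise with probability p, independently of the others, and otherwise a fall. The number of points per picture is not given, so 100, 700 and 8,300 were used. The last is close to the rough total of 10^5 in SAP 4.3.1 divided over 12 pictures (100,000/12 ≈ 8,333), if that total refers to one set of 12 pictures.

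**Closed form for the literal rule in 6.11.3, p < 0.5.** The scored share is all rises plus falls made at the maximum size. In the long run the picture is at the maximum for a share 1 − p/(1 − p) of points. Hence

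scored = p + (1 − p) × [1 − p/(1 − p)] = p + (1 − p) − p = 1 − p.

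For p = 0.3, the share at the maximum is 1 − 0.3/0.7 = 0.571, and scored = 0.3 + 0.7 × 0.571 = 0.70. For p > 0.5 the picture soon leaves the maximum and scored ≈ p. Together, scored ≈ max(p, 1 − p).

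**Exact calculation over the 91 possible sizes:**

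| True share of rises p | 6.11.3 literal, 100 points | 6.11.3 literal, 700 points | 6.11.3 literal, 8,300 points | Minimum limit only (= p) | 4.3.1 as written (= 1 − p) |
|---|---|---|---|---|---|
| 0% | 100% | 100% | 100% | 0% | 100% |
| 30% | 70.7% | 70.1% | 70.0% | 30% | 70% |
| 40% | 62.0% | 60.3% | 60.0% | 40% | 60% |
| 50% | 57.5% | 52.9% | 50.9% | 50% | 50% |
| 60% | 62.0% | 60.3% | 60.0% | 60% | 40% |
| 70% | 70.7% | 70.1% | 70.0% | 70% | 30% |
| 100% | 100% | 100% | 100% | 100% | 0% |

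Under the literal rule the curve is symmetric, and only its trough depends on the number of points. At 700 points, a patient who improves from 30% to 50% would be plotted as declining from 70.1% to 52.9%. Under 4.3.1 the ordering is reversed, not tied. Only the version that credits rises, including those at the minimum, gives p.

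**Would settling the direction alone be enough?** No. If falls were success and both limits were still credited, rises at the minimum would be miscounted instead. For p > 0.5 the long-run share at the minimum is 1 − (1 − p)/p, so scored = (1 − p) + p × [1 − (1 − p)/p] = p, while for p < 0.5 it stays near 1 − p. That is the same symmetric shape.

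**Mean picture size** still separates the extremes: 1.00 at p = 0 against 0.50, 0.16 and 0.105 at p = 1 for 100, 700 and 8,300 points.

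**The case against.** The strongest reply is that the success sentence was meant for the minimum only. It follows directly on the minimum case, and its contrast fits a rise that the picture can no longer show; it makes little sense for a fall in a task whose goal is to rise. That may well be the intention. The text does not say so, however, and its grammar covers both cases, so clarification is still needed.

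Second, 4.3.1 already computes the measure from haemoglobin values over all sampling points and needs no rule for the limits. This stands, and it narrows the point: a reader might infer that percentage success cannot measure regulation at all, or that the best and worst regulators will be reported as equal. The documents do not support that, because the tie arises only under the literal reading of 6.11.3. Under 4.3.1 as written the score is reversed.

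Third, the measure has a small role. It is one of three shown graphically in 4.3.1. The modelling in 4.3.2 uses β values, the model in 4.3.3 uses mean picture size, and the primary analysis in 4.1 uses none of these. Section 4 treats the neurophysiological analyses as exploratory, and 4.3 calls its fNIRS plan temporary. All of this stands. It limits the consequence, and it also means that a further SAP version is already expected in which the text can be put right.

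Fourth, neighbouring haemoglobin samples are unlikely to be independent, and the documents give neither sampling rate nor picture duration. Serial correlation would change the middle of the curve, but not its values at p = 0 and p = 1. The 30% and 70% contrast is therefore illustrative.

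**Conclusion.** The point holds as a defect of definition. Taken literally, 6.11.3 scores failures at the maximum picture size as successes, and 6.11.3 and 4.3.1 disagree on direction, on handling of the limits and on the unit counted. With independent sampling points, the literal rule gives about max(p, 1 − p), lowest for patients at chance level, and 4.3.1 gives 1 − p. How far real patients would be misplaced depends on the serial correlation of the signal and on the spread of true shares, neither of which the documents give.

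The consequence is a potentially misleading descriptive display of regulation success. It would be wrong to infer that the efficacy result or the regulation–outcome model is affected; neither uses percentage success.

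**What to change.** Use one definition in both sections: percentage success is the number of sampling points at which oxygenated haemoglobin exceeded its predecessor, divided by all sampling points, computed from the recorded haemoglobin values whatever the picture size.

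- In 4.3.1, change the direction of the comparison from below to above the predecessor, to match the goal stated in 6.11.3.
- In 6.11.3, limit the success sentence to the minimum size: a further rise there counts as success, and a further fall at the maximum does not.
- In 6.11.3, name the sampling point as the unit, in place of the trial.

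The changes should be made together, since correcting either the direction or the limit rule alone leaves an error. The cost is a few words in two sections and one line of code, with no new data.
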